Power Calculation: A one-sample method was chosen to test the observed proportion against the expected proportion determined from the preliminary data of the percent of those who achieved these goals. Using the most stringent criteria above of 20% (session 12) versus 60% (session 36) who achieve the TUG goal, there is 100% power (alpha=5%, double sided Z-power=5.6) with 13 of 63 (20%) versus 38 of 64 (60%) achieving the goal. If the attrition rate is as high as 25%, then the power is still 100%, (alpha=5%, double sided Z-power=4.53), with 10 of 48 (20%) at session 12 versus 29 of 48 (60%) of the participants achieving the goal at session 36.

Secondary Hypotheses

1. Bowel function will improve as demonstrated by 25% improvement on the Ten-question bowel survey.
2. Total body fat mass is hypothesized to be reduced by 2.0 ± 1.2 kg

Power Calculation: The preliminary data demonstrated a total score change of 31.5 ± 7.1 to 22.5 ± 5.3 , N=8 and a total body fat mass change from 24.14 ± 8.45 to 22.22 ± 8.19 , N=9, alpha=0.05, using a pairwise method, the power for both was 100%. Allowing for 25% dropout, the power is still 100% for 48 participants at an alpha=0.05.

Please note, that both the primary and secondary hypotheses are well powered due to the huge effect observed in the preliminary data. However, performing this study in fewer participants will not permit us to ask many of the exploratory questions. There is no empirical data to support an appropriate power calculation for the exploratory hypotheses.

References

2. Spungen, A. M., Adkins, R. H., Bauman, W. A., Kemp, B. J. & Waters, R. L. The effects of level and completeness of lesion on body composition in subjects with spinal cord injury. *J Spinal Cord Med* **22**, 43 (1999).

3. Spungen, A. M., Wang, J., Pierson, R. N. & Bauman, W. A. Soft tissue body composition differences in monozygotic twins discordant for spinal cord injury. *J. Appl. Physiol.* **88**, 1310–5 (2000).
4. Wahman, K. *et al.* Cardiovascular disease risk factors in persons with paraplegia: the Stockholm spinal cord injury study. *J Rehabil Med* **42**, 272–278 (2010).

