# A Randomized, Crossover Clinical Trial of Exoskeletal-assisted Walking to Improve Mobility, Bowel Function and Cardio-Metabolic Profiles in Persons with SCI

## Statistical Plan and Data Analysis:

The best value achieved for each walking test during sessions 5 to 12 (T1) and from 13 to 36 (T2) will be recorded separately to be used for comparative analysis. These best T1 and T2 scores will be used to determine percent of occurrence with the hypothesized goals. Achievement of the hypothesized goals in the WALK intervention group for the primary outcomes (10mWT, 6minWT and TUG at the 12- and 36-session time points) will be reported as categorical data and presented as a percent of occurrence with the 95% upper and lower confidence intervals (CI). Continuous variables for the Secondary outcomes of the body composition and bowel function variables will be presented as mean  $\pm$ SD. For the continuous variables, a difference score or percent change from pre to post will be calculated for the WALK and UA arms of the study. Comparisons between WALK (Pre-Post) vs. UA (Pre-Post) difference scores will be performed using paired t-tests. Pre to post comparisons for variables that are not normally distributed will be performed by non-parametric tests such as the Wilcoxon signed rank test or the paired sign test.

**Walking outcomes (10mWT, 6minWT, and TUG):** Achievement of the hypothesized goals in the WALK intervention group will be reported as categorical data and presented as percent occurrence with 95% confidence intervals (CI). For each of these outcomes, the best value achieved during the T1 period (sessions 5-12) and the T2 period (sessions 13-36) will be recorded separately and compared to the hypothesized goals, as listed below:

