**Primary Hypothesis (are tested pre and post the WALK arm only):**

1. By session 36, 70% of the participants compared with 10% at session 12 will be able to perform the 10mWT  $\leq$ 40 seconds ( $\geq$ 0.25 m/s);
2. By session 36, 70% of the participants compared with 10% at session 12 will be able to perform the 6minWT distance  $\geq$ 80 m ( $\geq$ 0.22 m/s); and
3. By session 36, 60% of the participants compared with 20% at session 12 will be able to perform the TUGin  $\leq$ 90 seconds.

**Power Calculation:** A one-sample method was chosen to test the observed proportion against the expected proportion determined from the preliminary data of the percent of those who achieved these goals. Using the most stringent criteria above of 20% (session 12) versus 60% (session 36) who achieve the TUG goal, there is 100% power (alpha=5%, double sided Z-power=5.6) with 13 of 63 (20%) versus 38 of 64 (60%) achieving the goal. If the attrition rate is as high as 25%, then the power is still 100%, (alpha=5%, double sided Z-power=4.53), with 10 of 48 (20%) at session 12 versus 29 of 48 (60%) of the participants achieving the goal at session 36.

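### Three primary walking hypotheses, but no rule on whether one or all must succeed and no multiplicity adjustment

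*SAP*

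**What the plan says.** The SAP, under Statistical Plan and Data Analysis, names "the primary outcomes (10mWT, 6minWT and TUG at the 12- and 36-session time points" and says that achievement of each goal will be "presented as percent occurrence with 95% confidence intervals (CI". The next heading reads "Primary Hypothesis (are tested pre and post the WALK arm only", and under it stand three numbered hypotheses, each comparing session 36 with session 12:

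- 10mWT: 70% against 10%
- 6minWT: 70% against 10%
- TUG: 60% against 20%

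The Protocol carries the same list under Hypotheses and again in its own statistical section.

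For these outcomes, alpha is written only in the power calculation: "alpha=5%, double sided Z-power=5.6". That calculation covers TUG alone, chosen with the words "Using the most stringent criteria above", and it describes its method as follows: "A one-sample method was chosen to test the observed proportion against the expected proportion". It reports 100% power for 64 participants and again for 48.

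Neither document mentions a multiplicity adjustment, a testing order, a lead endpoint, or a rule for what counts as success on the primary objective.

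**The concern.** With three primary hypotheses and no rule, the meaning of a mixed result is left open. Suppose TUG reaches significance and the two speed-based tests do not. The plan does not say whether the primary objective has then been met. If the answer may be chosen after the data are seen, a single success out of three could be reported as a positive primary result, and the 5% in the power calculation would not be the error rate of that conclusion. The Protocol calls this a Phase III trial and says it is unknown whether a larger sample will match the ten-person pilot, so error control matters in the case where the large planned effects do not appear.

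**Working it through.** **Inputs.** From the SAP: three hypotheses; two-sided alpha 5% (written for TUG; taken to apply to the other two because TUG stands in for all three and every interval is at 95%); TUG rates 20% and 60%; the other two 10% and 70%; n=64, and n=48 after 25% attrition. Assumed: the correlation between the three test statistics, which the documents do not give.

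**1. The plan's own power figure.** Exact one-sample binomial test of 60% against a fixed 20%, upper tail at most 2.5%:

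- n=64: reject at 20 or more achievers (tail 2.2%). Power is above 99.99%.
- n=48: reject at 16 or more (tail 2.1%). Power is 99.99%.

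The stated 100% is reproduced. The printed Z-power values, 5.6 and 4.53, are not matched exactly. The nearest variants are the null-variance z minus 1.96 (5.70 and 4.79) and the same with continuity correction (5.54 and 4.61). This does not change the power.

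**2. Error rate if any one test suffices.** Independent tests: 1 − 0.95³ = 0.143. Counting only false improvement: 1 − 0.975³ = 0.073. For correlated tests, take three normal statistics with equal pairwise correlation and compute 1 − P(all three |Z| ≤ 1.96), or 1 − P(all three Z ≤ 1.96) for improvement only.

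| Correlation | Any two-sided rejection | Any false improvement |
|---|---|---|
| 0 | 14.3% | 7.3% |
| 0.5 | 12.5% | 6.3% |
| 0.7 | 10.9% | 5.5% |
| 0.8 | 9.8% | 4.9% |
| 0.9 | 8.4% | 4.2% |
| 0.95 | 7.3% | 3.7% |

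The single-test references are 5% and 2.5%.

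**3. Error rate if all three must succeed.** A false overall claim of improvement requires every test to reject, including any whose null is true. Its probability is therefore at most 2.5%, whatever the correlation.

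**4. Error rate after adjustment.** The first Holm step is 0.05/3 = 1.67%. When all three nulls are true, the chance of any two-sided rejection is 4.9% at correlation 0, 4.5% at 0.5 and 3.0% at 0.9.

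**5. Power for TUG at 1.67%.**

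*One-sample method, as in the plan.* The thresholds become 22 of 64 and 18 of 48. Power is above 99.9% and 99.95% respectively.

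*Exact McNemar test, since the same people are measured twice.* If T1 and T2 success are independent (an assumption), the probability of a gain is 0.60 × 0.80 = 0.48 and of a loss 0.20 × 0.40 = 0.08.

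| n | Power at 5% | Power at 1.67% |
|---|---|---|
| 64 | 99.6% | 98.5% |
| 48 | 97.3% | 92.9% |

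Independence is not an extreme case. If every session-12 achiever achieves again (gain 0.40, loss 0), power at n=48 and 1.67% is above 99.9%. If none does (gain 0.60, loss 0.20), which is implausible, it is 74.8%.

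*The 10% against 70% hypotheses* stay above 99.9% at n=48 and 1.67%, by the one-sample method and by McNemar under independence.

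**The case against.** The strongest reply is that nothing in the plan says one success is enough. The heading is singular, the three items are joined as a list, and powering on the smallest contrast fits a requirement that all three succeed at least as well. Under that rule no adjustment is needed. This stands, and it is why the defect is the missing rule rather than a proven inflation. It does not close the point, because the all-three rule is not written either and cannot be supplied after the data are seen.

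A reader might infer that the primary error rate simply is 11% to 14% instead of 5%. The documents do not support that. The range needs the any-one rule, a correlation between 0 and about 0.7, and rejections counted in both directions. Two of the three goals are speed thresholds met by the same person in the same device, so a higher correlation is plausible, and 11% is not a lower bound.

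It is also fair that the analysis text promises percentages with intervals and names no T1-against-T2 test for the walking outcomes. Testing at 5% for 10mWT and 6minWT is therefore inferred. The hypotheses are nevertheless said to be tested, and the power calculation names a test, so the inference is reasonable.

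Finally, a reader might infer that Holm cuts TUG power from 100% to about 92%. That sets a one-sample figure against a paired one. Like for like, the McNemar loss at n=48 is 97.3 − 92.9 = 4.4 points under independence.

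**Conclusion.** The gap is real: three primary hypotheses, no success rule and no adjustment. Its size depends on the rule eventually applied. Under an any-one rule, the two-sided familywise error is up to 14.3%, or about 7% to 14% for correlations from 0.95 to 0, and false claims of improvement run at about 4% to 7% against 2.5%. Under an all-three rule there is no inflation. These figures assume normal test statistics with equal correlation and 5% applied to each hypothesis. At the planned effects an adjustment would change little; it matters if those effects fail to appear. The remedy is worth making because it is cheap and settles the meaning of a mixed result in advance.

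One limit should be stated with it. T1 is the best value over sessions 5 to 12 (8 sessions) and T2 the best over sessions 13 to 36 (24 sessions). That favours T2 even without true change. It is a separate issue, and a multiplicity adjustment does not correct it, so Holm should not be read as guaranteeing a true 5%.

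**What to change.** Add one of two sentences to the SAP, and the same to the Protocol's statistical section:

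- *Each primary hypothesis may be claimed separately; the three are tested with the Holm procedure at a familywise two-sided 5%.*
- Or: *The primary objective is met only if all three hypotheses are rejected, each at two-sided 5%.*

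Either sentence should name the test it applies to, since the analysis text currently gives only intervals.

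If Holm is chosen, restate TUG power at the 1.67% step, giving the method and the assumed link between T1 and T2 success. This is conservative: if the planned effects hold, the other two hypotheses would usually be rejected first and TUG tested at a later, less strict step.

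The cost is SAP wording and slightly lower stated power, with no added participants, visits or data. The all-three rule needs no change of alpha, but a miss on any one test then means the primary objective is not met.

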## Secondary Hypotheses

1. Bowel function will improve as demonstrated by 25% improvement on the Ten-question bowel survey.
2. Total body fat mass is hypothesized to be reduced by  $2.0 \pm 1.2$  kg

**Power Calculation:** The preliminary data demonstrated a total score change of  $31.5 \pm 7.1$  to  $22.5 \pm 5.3$ , N=8 and a total body fat mass change from  $24.14 \pm 8.45$  to  $22.22 \pm 8.19$ , N=9, alpha=0.05, using a pairwise method, the power for both was 100%. Allowing for 25% dropout, the power is still 100% for 48 participants at an alpha=0.05.

Please note, that both the primary and secondary hypotheses are well powered due to the huge effect observed in the preliminary data. However, performing this study in fewer participants will not permit us to ask many of the exploratory questions. There is no empirical data to support an appropriate power calculation for the exploratory hypotheses.
